2. STUDY OBJECTIVES

Primary outcome: % time spent in hypoglycaemia (<3.0mmol/L, 55mg/dL)

Secondary outcome: Number of episode of serious hypoglycaemia (defined as a sensor glucose <3.0mmol/L (55mg/dL) for >20 minutes)

% time spent in hypoglycaemia (<3.9mmol/L, 70mg/dL)

% time in euglycaemia (3.9-7.8mmol/L, 70-140mg/dL)

% time spent in target (3.9-10mmol/L, 70-180mg/dL)

% time spent in hyperglycaemia (>10mmol/L, 180mg/dL)

Number hypoglycaemic excursions

Severe hypoglycaemia

MAD%

Glucose variability

HbA1c

Ambulance call-out rates

Diabetes treatment satisfaction questionnaire

CGM usability

PAID

Gold score

Fear of hypoglycaemia survey score (HFS2)

Cost effectiveness

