6. ASSESSMENT AND FOLLOW-UP

6.1 CLINIC VISIT 1: Screening and Randomisation

Following informed consent study participants will give a full medical and medication history, as well as undergo a physical examination and ECG. Venous blood tests will be taken and sent to assess HbA1c, plasma glucose, renal function, serum C-peptide, thyroid function test, 9 am cortisol and coeliac screen (tissue transglutaminase antibody). Women of childbearing age will have a urine pregnancy test. If participants meet the inclusion criteria they will be enrolled on to the study and will complete a semi-structured participant interview and questionnaires (Diabetes treatment satisfaction questionnaire, CGM usability, PAID, and Fear of hypoglycaemia survey score (HFS2)). A Gold Score questionnaire will also be completed.

Participants enrolled will be randomised to real-time continuous glucose monitoring (RT CGM) or self-monitoring blood glucose (SMBG) group. Randomisation will be done using sealedenvelope.com and stratified by insulin delivery modality.

The RT CGM group will receive a Dexcom G6 transmitter and sensors, as well as a structured education refresher focusing on hypoglycaemia avoidance, recognition, and management. Participants in the SMBG group will receive the same structured education refresher focusing on hypoglycaemia avoidance, recognition, and management. All education will be delivered by the research nurse from a predefined curriculum and will be supported by independent written materials.

Participants will be instructed to test their capillary blood glucose if symptoms of hypo- or hyperglycaemia occur, in case of sensor failure or if the sensor glucose is out of the desired range. Participants using the G6 sensor will change sensor every ten days (or sooner in the event of sensor failure). Low glucose alert settings will be standardised at 4.4 mmol/L (80mg/dL) for all participants at the start of the study and can be reduced to 4 mmol/L (70mg/dL) at week 2 during the telephone visit depending on participant preference. High glucose alerts may be personalised.

The SMBG group will additionally undergo blinded CGM at weeks 1 and 2, weeks 4 to 6 and weeks 9 to 12 using the Dexcom G6 system. Participants in this group will be shown how to insert the Dexcom G6 at the first clinic visit and sensors provided so they can do this at home.

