6.2 FOLLOW-UP: Telephone follow-up during study period

Participants will be provided telephone support twice in the first week, then weekly for the next 3 weeks, and every 2 weeks thereafter, to optimise glucose and reduce the risk of further hypoglycaemia.

Participants in the CGM group with an iOS or Android smartphone will be able to upload and share data with the Research team through the “Dexcom Share app”. Participants who do not have a smartphone can upload their CGM data to an online platform named “Tidepool” using a PC or Mac desktop computer. In total, participants will use CGM for 12 weeks.

Participants in the SMBG group will be asked to self-monitor a minimum of 4 times daily and upload data to Tidepool, an online not-for-profit platform for individuals to selectively share data with clinicians to optimise diabetes management. They will receive telephone support from the research team, based on their Tidepool data, at the same time points as the RT-CGM group to optimise glucose and reduce the risk of further hypoglycaemia. Blinded CGM data from the SMBG group will be uploaded at the end of week 2, end of week 6 and end of week 12.

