7. STATISTICS AND DATA ANALYSIS

Baseline data will be taken from the first 14 days of monitoring and outcomes will be calculated from the last 30 days of the treatment period.

Power calculation: Based on findings from our 'I HART CGM trial', we would expect percentage time spent in hypoglycaemia (<3.0mM) to be 64% lower in the CGM group compared to the self-monitoring group [mean (SD): CGM group 2.1% (2.3%); self-monitoring group 5.8% (5.9%)]. To demonstrate that difference as significant at $p<0.05$ and with 80% power, 25 participants would be needed in each group. To allow for a 10% drop-out 55 participants will be recruited.

Analysis: Intention to treat. The primary outcome will be assessed by two-tailed unpaired t-test. For secondary outcomes, parametric data will be compared between the two study arms by two-tailed unpaired t-test for continuous variables. Non-parametric data will be compared using a Wilcoxon Rank sum test.

Sub-analysis: Other outcomes assessed will include hypoglycaemia awareness by participant (Gold score). Hypoglycaemia outcomes will be assessed throughout the time period and nocturnal only.

Data and all appropriate documentation will be stored for a minimum of 10 years after the completion of the study, including the follow-up period.

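### Sensor-defined hypoglycaemia episodes are listed as plain numbers with no wear-time denominator, over a period that section 7 leaves undefined and for which scheduled sensor days differ by arm

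*Combined protocol and SAP*

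**What the plan says.** Section 7 sets the main windows (the last word of the sentence is left off here): "Baseline data will be taken from the first 14 days of monitoring and outcomes will be calculated from the last 30 days of the treatment". Under its sub-analysis heading it adds: "Hypoglycaemia outcomes will be assessed throughout the time period and nocturnal only". The period in that sentence is not defined.

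The arms do not wear sensors for the same time. For the RT-CGM arm, section 6.2 states: "In total, participants will use CGM for 12 weeks". For the control arm, section 6.1 states: "The SMBG group will additionally undergo blinded CGM at weeks 1 and 2, weeks 4 to 6 and weeks 9 to 12". Section 6.2 confirms the three blocks: "Blinded CGM data from the SMBG group will be uploaded at the end of week 2, end of week 6 and end of week 12". The blinded-download row of Appendix 1 agrees.

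Section 2 includes two sensor outcomes named as numbers: "Number of episode of serious hypoglycaemia (defined as a sensor glucose <3.0mmol/L (55mg/dL) for >20 minutes"), and "Number hypoglycaemic excursions". Section 7 compares secondary outcomes by unpaired t-test or Wilcoxon rank sum test. The documents give no per-day or per-week denominator, minimum wear time, exposure offset or matching of weeks between arms.

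**The concern.** A number of episodes can be compared between arms only if both arms were observed for the same time, or if the number is divided by the time observed. Here the observation time differs by design, and neither of the named tests adjusts for it. The arm with more sensor days will record more episodes at the same underlying rate. That arm is RT-CGM, so raw counts would understate a benefit and could show an excess where none exists.

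The frequency of hypoglycaemia is a stated aim and part of the hypothesis, so these outcomes matter even though they are secondary. The trial is open-label. If the window and denominator are left open, they may be chosen after the data have been seen.

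**Working it through.** The plan states no figure for sensor exposure, so there is none to reproduce. Its planning reduction, used in step 4, does reproduce: (5.8 − 2.1) / 5.8 = 63.8%, which section 7 gives as 64%.

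**Step 1. Scheduled sensor days over 12 weeks** (sections 6.1 and 6.2)

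- RT-CGM: 12 × 7 = 84 days.
- SMBG: weeks 1–2, 4–6 and 9–12 = 14 + 21 + 28 = 63 days.
- Not sampled in the SMBG arm: weeks 3, 7 and 8 = 21 days, and 21 / 84 = 25% of the period.

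**Step 2. Scheduled sensor days in the last 30 days** (section 7)

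- The window is days 55 to 84, so RT-CGM has 30 days.
- The last SMBG block, weeks 9–12, is days 57 to 84, so SMBG has 28 days. Days 55 and 56 fall in week 8.

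**Step 3. Effect on raw counts at equal true rates**

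Expected count = rate × days, so the ratio of counts equals the ratio of days.

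| Reading of the period | RT-CGM days | SMBG days | Count ratio at equal rates | Rate reduction needed for counts to tie |
|---|---|---|---|---|
| Full 12 weeks | 84 | 63 | 84 / 63 = 1.33 | 1 − 63/84 = 25% |
| Last 30 days | 30 | 28 | 30 / 28 = 1.07 | 1 − 28/30 = 6.7% |

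If weeks 1–2 were set aside as baseline and the rest used, the days would be 70 and 49, a ratio of 1.43. The plan does not name that window, so it is left out of the range quoted.

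**Step 4. Effect on a true benefit**

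Assume, for illustration only, that the episode rate falls by the planning reduction for percentage time, so that the rate ratio is 2.1 / 5.8 = 0.362.

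- 12 weeks: 0.362 × 1.333 = 0.483, an apparent reduction of 51.7%.
- Last 30 days: 0.362 × 1.071 = 0.388, an apparent reduction of 61.2%.

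**Step 5. Do the different weeks distort percentages or rates?**

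These are already divided by wear time, so only the choice of weeks could matter. The mean sampled week is 6.67 in the SMBG arm, against 6.50 for weeks 1–12. Take an assumed smooth trend in which hypoglycaemia in week w is proportional to exp[r(w − 1)]. The SMBG mean over its nine sampled weeks, divided by its mean over all 12, is:

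| r per week | Sampled mean / 12-week mean |
|---|---|
| −0.20 | 1.010 |
| −0.10 | 0.995 |
| −0.05 | 0.995 |
| +0.05 | 1.011 |
| +0.10 | 1.028 |

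The distortion runs from about −0.5% to +3%, small beside the effect on raw counts over 12 weeks.

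**Step 6. After the fix**

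Dividing by sensor days removes the exposure ratio on either reading. Restricting RT-CGM to weeks 1–2, 4–6 and 9–12 gives 63 against 63 days, a ratio of 1.0.

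**The case against.** The strongest reply is that the disputed sentence pairs its period with night-time only, and so may mean no more than all hours against night hours within the 30-day window that section 7 has already set. That reading is natural, and on it the ratio is 1.07 rather than 1.33. It cannot be ruled out. Nor can the 12-week reading, because the same section names the last 30 days explicitly elsewhere and uses different words here. Neither reading gives equal scheduled exposure.

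A second reply is that section 2 only names outcomes, and that an analyst might well report rates. This stands in part: no raw-count comparison is stated. But the outcomes are called numbers and the tests carry no exposure term, so following the text literally gives raw counts.

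Third, any bias runs against RT-CGM and could not create a false benefit. That is correct. It limits the harm but does not make the comparison sound.

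A reader might also infer more than the documents support:

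- **That percentages are compared unfairly because the weeks differ.** Step 5 shows little effect under smooth trends.
- **That the weeks just after the index episode cannot be compared.** Weeks 1–2 and 4–6 are scheduled in both arms, which is five of the first six weeks.
- **That Appendix 1 contradicts the block schedule.** Its insertion row is shared by both arms, and its separate blinded-download row agrees with sections 6.1 and 6.2. Splitting the row would be tidying only.

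**Conclusion.** The point holds in a conditional form. The period for the hypoglycaemia sub-analysis is undefined, and two sensor outcomes have no denominator although scheduled wear differs by arm. If these outcomes are compared as raw numbers, they are biased against RT-CGM by about 7% (last 30 days) to 33% (12 weeks) at equal true rates.

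The range assumes that wear follows the schedule in both arms. Actual wear may differ, which is a further reason to divide by it. The apparent reductions in step 4 also assume that the planning effect on percentage time carries over to episode rates.

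The documents do not support saying that the plan, as written, inflates RT-CGM episodes by 33%. That needs both the 12-week reading and unnormalised counts, and the plan commits to neither. The primary outcome and other percentage-time outcomes are not materially affected. Severe hypoglycaemia, ambulance call-outs and the Gold score need no sensor and are unaffected, as is the sample size.

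**What to change.** Amend section 7 in three respects before any data are compared by arm:

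1. **Period.** State whether the sub-analysis covers the full 12 weeks or all hours of the last 30 days, with night-time as a subset of whichever is chosen.
2. **Denominator.** Analyse episodes of serious hypoglycaemia and hypoglycaemic excursions as a rate per day or week of sensor wear. The planned t-test or rank sum test can be applied to each participant's rate. Alternatively, use a count model with log wear time as an offset. This is needed whichever period is meant.
3. **Matched weeks.** If 12 weeks is meant, compare the arms over weeks 1–2, 4–6 and 9–12, at least as a sensitivity analysis.

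The cost is a few sentences, with no extra participants, visits or sensors. The matched-weeks comparison leaves out up to 21 days (25%) of RT-CGM data per participant, which can still be described within that arm. Given step 5, the denominator is the essential change and the matched weeks are a safeguard.

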8. REGULATORY ISSUES

8.1 ETHICS APPROVAL

The Study Coordination Centre has obtained approval from the **xxx** Research Ethics Committee (REC) and Health Research Authority (HRA). The study must also receive confirmation of capacity and capability from each participating NHS Trust before accepting participants into the study or any research activity is carried out. The study will be conducted in accordance with the recommendations for physicians involved in research on human subjects adopted by the 18th World Medical Assembly, Helsinki 1964 and later revisions.

8.2 CONSENT

Consent to enter the study must be sought from each participant only after a full explanation has been given, an information leaflet offered and time allowed for consideration. Signed participant consent should be obtained. The right of the participant to refuse to participate without giving reasons must be respected. After the participant has entered the study the clinician remains free to give alternative treatment to that specified in the protocol at any stage if he/she feels it is in the participant's best interest, but the reasons for doing so should be recorded. In these cases, the participants remain within the study for the purposes of follow-up and data analysis. All participants are free to withdraw at any time from the protocol treatment without giving reasons and without prejudicing further treatment.

8.3 CONFIDENTIALITY

The Chief Investigator will preserve the confidentiality of participants taking part in the study and is registered under the Data Protection Act. Confidentiality of data will be preserved during data transmission via the use of anonymised codes. Participants will be assigned codes based on order of enrolment and site at which they are enrolled (AIR-HH-001 etc. for those enrolled at Hammersmith Hospital, AIR-CX-001 etc. for those enrolled at Charing Cross Hospital and AIR-SM-001 etc. for those enrolled at St Mary's Hospital). Identifiable personal information will be stored securely in a locked room at Imperial College Healthcare NHS Trust. Anonymised data will be held securely in swipe-card access room at Imperial College London and on Imperial College London computers. The latter will be encrypted with a password. Data will be accessible only to the Research Team and for audit. Pseudoanonymised data will be used for analysis. Confidentiality of data will be preserved when sending identifiable information from Imperial College Healthcare NHS trust and London Ambulance Service to the Imperial College London research team by using encrypted NHS.net email accounts. The data will be stored at Imperial College London for 10 years. App security is covered in Tidepool's privacy statement as they are a separate data controller. The data custodian is [name].

8.4 INDEMNITY

Imperial College London holds negligent harm and non-negligent harm insurance policies which apply to this study.

8.5 SPONSOR

Imperial College London will act as the main Sponsor for this study. Delegated responsibilities will be assigned to the NHS trusts taking part in this study.

8.6 FUNDING

Dexcom are funding this study. Participants will be fully reimbursed for travel expenses.

8.7 AUDITS

The study may be subject to inspection and audit by Imperial College London under their remit as sponsor and other regulatory bodies to ensure adherence to GCP and the NHS Research Governance Framework for Health and Social Care (2nd edition).

9. STUDY MANAGEMENT

The day-to-day management of the study will be co-ordinated through the Chief Investigator, [name].

10. PUBLICATION POLICY

Data from the study will be analysed then published in peer-reviewed scientific journals and presented at Scientific Conferences. A lay summary of the data will be disseminated to all participants and a summary of results will be publically available.

11. APPENDICES

- Summary of investigations, treatment and assessments
- Dexcom G6 instructions for use
- Validated questionnaires:
 - Diabetes treatment satisfaction questionnaire
 - CGM usability
 - PAID
 - Gold score
 - Fear of hypoglycaemia survey score (HFS2)

Tidepool Privacy Statement (<https://tidepool.org/legal/privacy-policy-2-0/>)

Appendix 1: Summary of investigations, treatment and assessments

	Clinic Visit 1 (Screening & Randomisation)	End of Week											Week 12 (Clinic Visit 2)
		1	2	3	4	5	6	7	8	9	10	11	
History	x												
Medication history	x												
ECG	x												
Physical examination	x												
Urine pregnancy test	x												
HbA1c	x												x
Glucose	x												
Renal function	x												
TFT	x												
9am cortisol	x												
Coeliac screen	x												
C-peptide	x												
Gold Score	x												x
Participant interview	x												x
QoL Questionnaires	x												x
Diabetes Education	x												
Randomisation	x												
CGM education	x												
CGM insertion	x	x	x	x	x	x	x	x	x	x	x	x	
Telephone consultation		x (twice)	x	x	x		x		x		x		
CGM group - CGM download		x (twice)	x	x	x		x		x		x		x
SMBG Group - Meter download		x (twice)	x	x	x		x		x		x		x
SMBG Group - Blinded CGM download			x				x						x
Research clinic visit	x												x
